7.3. Treatment-Emergent Adverse Events and Serious Adverse Events

The definitions of a TEAE (solicited and unsolicited), MAAE and SAE can be found in Appendix 3 (Section 9.3).

The Investigator and any qualified designees are responsible for detecting, documenting, and recording events that meet the definition of a TEAE (solicited and unsolicited), MAAE, or SAE. Investigators remain responsible for following up TEAEs, MAAEs, SAEs and other reportable safety events for outcome.

7.3.1. Time Period and Frequency for Collecting TEAE, MAAE SAE and Other Reportable Safety Event Information

All TEAEs (solicited and unsolicited), MAAEs, SAEs and other reportable safety events that occur after the consent form is signed but before study administration must be reported by the Investigator if the event cause the participant to be excluded from the study or is the result of a protocol-specified intervention, including but not limited to washout or discontinuation of usual therapy, diet, or a procedure.

Table 7 below summarizes the different reporting timelines for TEAEs (unsolicited and solicited), MAAE, SAEs, SUSAR, and pregnancy.

Medical occurrences that begin before the start of study drug but after obtaining informed consent will be recorded on the Medical History/Current Medical Conditions section of the eCRF not the AE section.

All SAEs will be recorded and reported to the Sponsor or designee immediately and under no circumstance should this exceed 24 hours from awareness, as indicated in Appendix 3 (Section 9.3). The Investigator will submit any updated SAE data to the Sponsor within 24 hours of it being available.

Table 7Adverse Event Reporting Timelines to the Sponsor

Type of Event	TEAE (unsolicited)	TEAE (solicited)	MAAE	SAE / SUSAR	Pregnancy
Reporting period	From first dose until 4 weeks after last dose of study drug	l week after each study drug administration	From first dose until EOS	From first dose until EOS.	From first dose until EOS
Reporting Timelines to the Sponsor	Entered into the clinical database on an ongoing basis	Entered into the clinical database on an ongoing basis	Within 24 hours	Within 24 hours	Within 24 hours
Reporting Method	AE eCRF	Solicited Symptom Diary	AE eCRF	AE eCRF	Pregnancy form

Abbreviations: AE = adverse event; eCRF = electronic Case Report Form; EOS = end of study; MAAE = medically attended adverse event; SAE = serious adverse event; SUSAR = suspected unexpected serious adverse reaction; TEAE = treatment-emergent adverse event

7.3.2. Method of Detecting TEAEs, MAAEs and SAEs

Appendix 3 provides the method of recording (Section 9.3.4), evaluating severity (Section 9.3.4.1), and assessing causality (Section 9.3.4.2) of AEs, MAAEs and SAEs and the procedures for completing and transmitting SAE reports (Section 9.3.5).

Care will be taken not to introduce bias when detecting AEs, MAAEs and/or SAEs. Open-ended and non-leading verbal questioning of the participant is the preferred method to inquire about AE occurrences.

7.3.3. Follow-up of AEs, MAAEs and SAEs

The Investigator is obligated to perform or arrange for the conduct of supplemental measurements and evaluations as medically indicated to elucidate the nature and causality of the AE, MAAE, or SAE as fully as possible. This may include laboratory tests or investigations, histopathological examinations, or consultation with other health care professionals.

New or updated information will be recorded in the originally submitted documents.

The Investigator will submit any updated SAE data to the Sponsor within 24 hours of receipt of the information.

AEs, including pregnancy, will be followed by the Investigator as specified in Appendix 4.

7.3.4. Regulatory Reporting Requirements for SAEs

- Prompt notification by the Investigator to the Sponsor of a SAE is essential so that legal obligations and ethical responsibilities towards the safety of participants and the safety of the study drug under clinical investigation are met.
- The Sponsor has a legal responsibility to notify both the local regulatory authority and other regulatory agencies about the safety of the study drug under clinical investigation. The Sponsor will comply with country-specific regulatory requirements relating to safety reporting to the regulatory authority, Institutional Review Boards (IRBs)/Independent Ethics Committees (IECs), and Investigators.
- For all studies, Investigator safety reports must be prepared for SUSAR according to local regulatory requirements and Sponsor policy and forwarded to Investigators as necessary.
- An Investigator who receives an Investigator safety report describing a SAE or other specific safety information (e.g., summary or listing of SAEs) from the Sponsor will review and then file it along with the Investigator's Brochure (IB) and will notify the IRB/IEC, if appropriate according to local requirements.

7.3.5. Death Events

Events resulting in death will be an SAE regardless of association to study drug. Death is an outcome and should not be reported as an event term. The event that leads to the death should be reported as the SAE term.

7.3.6. Pregnancy

• In the case of a positive confirmed pregnancy, the participant will be withdrawn from administration of study drug but may remain in the study.

- Details of all pregnancies in female participants and female partners of male participants will be collected as outlined in Appendix 4 (Section 9.4).
- If a pregnancy is reported, the Investigator should inform the Sponsor within 24 hours of learning of the pregnancy and should follow the procedures outlined in Appendix 4 (Section 9.4).
- Abnormal pregnancy outcomes (e.g., spontaneous abortion, fetal death, stillbirth, congenital anomalies, ectopic pregnancy) are considered SAEs.

8. STATISTICAL CONSIDERATIONS

8.1. Sample Size Determination

8.1.1. Part 1

Part 1 is an open-label, lead in, repeat-dose, dose and age escalation design to evaluate the VXA-COV2-1.1-S oral vaccine in two cohorts with repeat dose administration. Cohort 1 will enroll approximately a total of 36 healthy adult participants that are naive (no prior vaccination against SARS-CoV-2 infection and no history of prior COVID-19 or SARS-CoV-2 infection) across 3 groups of 12 subjects each, encompassing 2 age groups and two dose levels. Cohort 2 will enroll approximately a total of 36 healthy adult participants who have received two doses of an EUA or FDA approved mRNA vaccine for the prevention of SARS-CoV-2 infection across 3 groups of 12 subjects each, encompassing 2 age groups and two dose levels.

There are no sample size calculations utilized for Part 1; the cohort size is estimated to provide informative safety and immunogenicity data to allow dose selection for safely proceeding to Part 2.

8.1.2. Part 2

The number of participants to be randomized in Part 2 (VXA-CoV2-1.1-S and placebo) is predicted to yield meaningful immunogenicity and efficacy results to inform how best to proceed into later stage studies. In previous human studies with Ad5 vectored oral tableted vaccines using the same vaccine platform (Ad5 vectored vaccine coding for target virus-specific antigens and a dsDNA adjuvant), the vaccine was well tolerated at total doses up to $2x10^{11}$ IU.

All testing will be performed at alpha = 0.05. All tests will be two-sided. Assuming attack rate in unvaccinated group (ARU) = 5% and vaccine efficacy (VE) = 90%, 341 participants would be required per treatment arm, yielding 95% power.

The total sample size for Part 2 of this study (2 arms) would be 682. To allow for a $\sim 15\%$ dropout rate, 800 participants will be randomized.

2-sided Alpha	0.05	0.05	0.05	0.05	0.05	0.05	0.05	0.05
ARU	5%	5%	5%	5%	5%	5%	5%	5%
VE	90%	90%	90%	90%	95%	95%	95%	95%
Power	80%	85%	90%	95%	80%	85%	90%	95%
SS/Arm	207	236	276	341	177	202	236	292
Sample Size (part 2 of								
study, two arms)	414		472	682	354	404	472	584

Unvaccinated Atta	ck Rate (ARU): 5%
--------------------------	-------------------

Interim looks at the efficacy using O'Brien Fleming Boundaries. One interim analysis may be conducted during the study by the IDMC if 18 confirmed cases of COVID-19 are observed prior to the completion of Month 7 visits, 6 months following the second vaccination, by all subjects. Given a power estimate of 95%, the study may be stopped by the Sponsor for overwhelming efficacy at the interim look if alpha ≤ 0.003 . The study will continue if this criterion is not met (and may be continued even if it is met per Sponsor's review and FDA agreement). If the decision is made to continue the study until completion at 6 months post last vaccination, alpha ≤ 0.05 .

Analysis Population	Description
Screened	All subjects who enter screening (assigned a screening number)
Randomized	All participants who are assigned a randomization number
Dose 1 evaluable immunogenicity	All eligible randomized participants who receive the study intervention to which they are randomly assigned at the first dose, have at least 1 valid and determinate immunogenicity result after Dose 1, have blood collection within an appropriate window after Dose 1, and have no other important protocol deviations.
Dose 2 evaluable immunogenicity	All eligible randomized participants who receive 2 doses of the study intervention to which they are randomly assigned, within the predefined window, have at least 1 valid and determinate immunogenicity result after Dose 2, have blood collection within an appropriate window after Dose 2, and have no other important protocol deviations.
Dose 1 all-available immunogenicity	All randomized participants who receive at least 1 dose of the study intervention with at least 1 valid and determinate immunogenicity result after Dose 2.
Evaluable efficacy	All eligible randomized participants who receive all study intervention dose(s) as randomized within the predefined window and have no other important protocol deviations.
All-available efficacy	All randomized participants who receive at least 1 dose of the study intervention.
Safety	All randomized participants who receive at least 1 dose of the study drug.

8.2. **Populations for Analyses**

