- **Cohort 2-** Healthy adults who are prior vaccinated (have received two doses of an EUA or FDA approved mRNA COVID-19 vaccine at least 6 months prior to enrollment [Day 1] and are at low risk of developing severe COVID-19 upon potential infection with SARS-CoV-2

Approximately Seventy-two (72) subjects will be enrolled in a stepwise manner as outlined in Table 1.

Population	Cohort	VXA-CoV2-1.1-S Dose Levels*	Age (years)	Vaccination Timepoints	No. of Participants	
Naive	la	1×10^{10} I.U. ±0.5 log	18 - 55	Day 1 & Week 4	12	
Prior vaccinated	2a	1x10 ¹⁰ I.U. ±0.5 log	18 - 55	Day 1 & Week 4	12	
		IDMC Data Rev	view ¹		•	
Naive	1b	1x10 ¹¹ I.U. ±0.5 log	18 - 55	Day 1 & Week 4	12	
Naive	1c	$1x10^{10}$ I.U. ±0.5 log	56 - 75	Day 1 & Week 4	12	
Prior vaccinated	2b	$1x10^{11}$ I.U. ±0.5 log	18 - 55	Day 1 & Week 4	12	
Prior vaccinated 2c 1×10^{10} I.U. $\pm 0.5 \log$ 56 - 75 Day 1 & Week 4 12						
IDMC Data Review ²						

Table 1Part 1 Groups, Doses and Sample Size

*Multiple tablets may be administered to deliver the full intended dose.

IDMC = Independent Data Monitoring Committee.

¹ IDMC to review safety data through Week 1 for 12 subjects in group a before enrollment will begin in b and c.

² IDMC to review safety data for all subjects within each age group and initial immunogenicity data from Part 1 to make recommendations to Sponsor on dose selection for randomized, placebo-controlled phase, before enrollment begins in Part 2.

Cohorts 1 and 2 (naïve and prior vaccinated subjects, respectively) will enroll in parallel. The IDMC may review safety data for the subgroups within each of these two cohorts separately if the enrollment rates between the two cohorts vary.

Duration of Study Participation

For each participant in Part 1 the duration of study activities is expected to last as follows:

Study Period (Part 1)	Duration
Screening Period:	30 days
Active Period:	8 weeks*
Safety Follow-up Period:	11 months
Total duration of participation:	~14 months

*Participants who discontinue study drug early will enter the Safety Follow-up Period at Week 4.

Part 2 – Randomized, Double-blind, Placebo-controlled (N = 800 Participants)

Healthy male and female adult volunteers 18 to 75 years old (inclusive) will be randomized in Part 2 as outlined in Table 2. A minimum of 200 of the total 800 participants in Part 2 will be >55 years of age.

Table 2	Part 2 - Treatment Arms, Dose and	Sample Size
	i ui c 2 i i cucinicite i initity 2005c und	Sumple Sile

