3.2.1. Part 1: Enrollment and Initial Vaccination

On Day 1, eligible participants will be enrolled sequentially to receive their 1st oral vaccination according to their assigned treatment group as specified in Table 1.

Population	Cohort	VXA-CoV2-1.1-S Dose Levels*	Age (years)	No of Doses	No. of Participants
Naive	1a	Low Dose: $1x10^{10}$ I.U. $\pm 0.5 \log$	18 - 55	2	12
Prior vaccinated	2a	Low Dose: $1x10^{10}$ I.U. $\pm 0.5 \log$	18 - 55	2	12
IDMC Data Review ¹					
Naive	1b	High Dose: 1x10 ¹¹ I.U. ±0.5 log	18 - 55	2	12
Naive	1c	Low Dose: $1x10^{10}$ I.U. $\pm 0.5 \log$	56 - 75	2	12
Prior vaccinated	2b	High Dose: 1×10^{11} I.U. $\pm 0.5 \log$	18 - 55	2	12
Prior vaccinated	2c	Low Dose: $1x10^{10}$ I.U. $\pm 0.5 \log$	56 - 75	2	12
	IDMC Data Review ²				

* Multiple tablets may be administered to deliver the full intended dose.

[†] Doses will be administered on Day 1 and Week 4.

¹ IDMC to review safety data through Week 1 for 12 subjects in a before enrollment will begin in b or c.

² IDMC to review safety data for all subjects within each age group and initial immunogenicity data from Part 1 to make recommendations to Sponsor on dose selection for randomized, placebo-controlled phase, before enrollment begins in Part 2

Cohorts 1 and 2 (naïve and prior vaccinated subjects, respectively) will enroll in parallel. The IDMC may review safety data for the subgroups within each of these two cohorts separately if the enrollment rates between the two cohorts vary.

During the Active Period, participants will record daily symptoms of reactogenicity for 1 week post each vaccination, administered on Day 1 and Week 4, using a Solicited Symptom Diary. They will return to the site at 1 and 4 weeks following each vaccination, as specified in the SoA, to have safety assessments and samples collected for evaluation of immunogenicity. Post completion of the Week 1 visit by all subjects in a specified cohort, as detailed in

Table 1, the IDMC will review Day 1 to Week 1 safety data and make recommendations as to whether to proceed to the next cohort(s). Upon completion of enrollment in Part 1, the IDMC will review safety and preliminary immunogenicity data from all cohorts and make recommendations to the Sponsor on the VXA-CoV2-1.1-S dose level to evaluate in Part 2. A summary of Part 1 safety and immunogenicity data with the intended dose for Part 2 will be submitted to FDA for review and concurrence prior to initiation of enrollment in Part 2.

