7.1.1. SARS-CoV-2 Infection and COVID-19 Diagnosis

Participants will be monitored for SARS-CoV-2 infection and/or symptomatic COVID-19 in the following manner:

- Testing for prior exposure by rapid antibody (Ab) test at Screening and Baseline (prevaccination) if Screening test >7 days prior to Baseline Visit (**Part 1 Cohort 1 only**).
- Testing by an FDA authorized rapid molecular test at any time a participant reports illness compatible with COVID-19 or reports known/ possible exposure to COVID-19. A sample will also be collected at Baseline to test for potential of pre-dose exposure should confirmation of negative infection be needed in participants who contract COVID-19 during the study.
- A negative onsite rapid molecular test is required prior to dosing at Days 1 and 29. This testing is needed given the high rates of COVID-19 being observed at clinical sites with the spread of Omicron variant.

Any participant reporting COVID-19 like illness or exposure to COVID-19 during the study will be asked to return to the site for an unscheduled visit to test for SARS-CoV-2 infection. Any FDA authorized rapid molecular test (e.g. LUCIRA COVID-19 Test) may be used for home or on-site testing for monitoring COVID-19 infection.. Participants with confirmed SARS-CoV-2 infection at any time during the study period will be asked to provide a nasal sample for rapid molecular test every two days after their confirmatory test until they test negative. The duration of q2day testing should end after 10 days if still testing positive at that time. They will also be monitored for clinical disease duration, severity, and outcome. The participant will be counseled

to notify their Primary Care Physician of their positive SARS-CoV-2 status and seek medical care should they become symptomatic.

The occurrence of virologically confirmed (by polymerase chain reaction [PCR] or rapid molecular test to SARS-CoV-2) symptomatic mild, moderate, or severe COVID-19 is defined in Table 5.

Subjects with confirmed COVID-19 will be evaluated for severity of disease as well as for the potential for vaccine-associated enhanced disease (VAED).

Mild	 At least one or more of the following: Fever (defined by subjective or objective measure, regardless of use of anti-pyretic medications)
wind	 New onset cough ≥ 2 COVID-19 respiratory/non-respiratory symptoms in Table 6 AND Does not meet criteria for moderate or severe disease

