	Geometric mean titers/concentrations (GMTs/GMCs) of SARS-CoV-2 neutralizing titers, S-binding IgG level, , and S-binding IgA levels serum, nasal and saliva), GMTs/GMCs and 2-sided 95% CIs and other reported antigens will be provided for by treatment group at the following time points:
	• Day 1, Week 4, Week 8, Optional (Month 7, and Month 13)
	• Geometric means will be calculated as the mean of the assay results after making the logarithm transformation and then exponentiating the mean to express results on the original scale. Two-sided 95% CIs will be obtained by taking natural log transforms of concentrations/titers, calculating the 95% CI with reference to the t-distribution, and then exponentiating the confidence limits.
	The geometric mean fold rise (GMFR) of SARS-CoV-2 neutralizing titers, S-binding IgG level, and S-binding IgA level. For SARS-CoV-2 neutralizing titers, S-binding IgG levels, and S-binding IgA levels, the GMFRs and 2-sided 95% CIs will be provided by treatment group at the following time points:
	• Week 4, Week 8, Optional (Month 7, and Month 13)
	GMFRs will be limited to participants with non-missing values prior to the first dose and at the postvaccination time point. The GMFR will be calculated as the mean of the difference of logarithmically transformed assay results (later time point – earlier time point) and exponentiating the mean. The associated 2-sided CIs will be obtained by calculating CIs using Student's t-distribution for the mean difference of the logarithmically transformed assay results and exponentiating the confidence limits.

Vaxart, l	Inc.
-----------	------

	Percentage of participants with ≥4-fold rise (or other assessments as per the SAP) in SARS-CoV-2 neutralizing titers, S1-binding IgG level, and RBD-binding IgG level will be summarized by treatment group at the following timepoints.
	• Week 4, Week 8, Optional (Month 7, and Month 13)
	For all the immunogenicity endpoints, the analysis will be based on the Dose 1 and Dose 2 evaluable immunogenicity populations. An additional analysis will be performed based on the all-available immunogenicity populations if there is a large enough difference in sample size between the all-available immunogenicity populations and the evaluable immunogenicity populations. Participants will be summarized according to the vaccine group to which they were randomized.
	Additional immunogenicity data will be assessed as per the SAP. Missing serology data will not be imputed.

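### No immunogenicity population or summary removes samples taken after an on-study SARS-CoV-2 infection or a non-study COVID-19 vaccine

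*Combined protocol and SAP*

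**What the plan says.** The populations table in Section 8.2 builds the Dose 1 and Dose 2 evaluable immunogenicity sets from eligibility, dosing as assigned, a valid result, sample timing and absence of important deviations. For Dose 2 the closing conditions are "have blood collection within an appropriate window after Dose 2, and have no other important protocol deviations". The all-available set asks for at least one dose, "with at least 1 valid and determinate immunogenicity result after Dose 2". None of the three names an on-study infection or another COVID-19 vaccine, and important deviations are not defined.

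Section 8.3.1 states that for all immunogenicity endpoints "the analysis will be based on the Dose 1 and Dose 2 evaluable immunogenicity populations"; Section 8.3.2 says the same for Part 2. The only data-handling rules given are that fold rises and within-participant ratios need non-missing values and that missing serology is not imputed.

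Other sections bear on how many such samples there will be:
- Section 7.1.1 requires a negative molecular test before each dose and explains: "This testing is needed given the high rates of COVID-19 being observed at clinical sites with the spread of Omicron variant".
- Sections 3.2.2, 4.2.2 and 6.2 keep participants who miss Dose 2 in immunogenicity follow-up.
- Section 5.9 offers placebo participants a COVID-19 vaccine after unblinding, while Section 8.3.2 still summarizes titers by arm at Month 13.

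Section 3.2.1 has the IDMC review preliminary immunogenicity data and "make recommendations to the Sponsor on the VXA-CoV2-1.1-S dose level to evaluate in Part 2".

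**The concern.** Antibodies to the spike protein rise after SARS-CoV-2 infection or another COVID-19 vaccine as well as after the study vaccine. A participant infected after Day 1 can therefore look like a strong responder. The efficacy analyses in Section 8.3.2 separate participants with and without evidence of infection; the immunogenicity analyses do not.

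In Part 1 the groups are small enough for one or two people to move a group mean, and these data may feed the choice of dose. In Part 2, if the vaccine works, infections collect in the placebo arm. Placebo titers then rise for reasons unrelated to study treatment, and the contrast a reader draws between the arms shrinks.

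**Working it through.** **1. The plan's own figures.** Part 1 is "across 3 groups of 12 subjects each, encompassing 2 age groups and two dose levels" in each of two cohorts: 2 × 3 × 12 = 72, as stated in Section 1.1. Section 8.1.1 adds: "There are no sample size calculations utilized for Part 1; the cohort size is estimated to provide informative safety and immunogenicity data". The only attack rate used to size the trial is the 5% in Section 8.1.2. With 5% against 0.5% (VE 90%), two-sided alpha 0.05, 95% power and pooled variance without continuity correction:

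n = [1.960 × √(2 × 0.0275 × 0.9725) + 1.645 × √(0.05 × 0.95 + 0.005 × 0.995)]² / 0.045² = 340.3, rounded up to 341 per arm, which matches the plan.

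**2. Which infected participants stay in.** A positive molecular test at Week 4 blocks Dose 2 unless the condition resolves within the 7-day window. Anyone who misses Dose 2 leaves the Dose 2 set. The test removes nobody from the Dose 1 set. It also leaves in the Dose 2 set those whose infection cleared before Day 29 or within the window, and everyone infected after Day 29. For Part 2 the safeguard is itself stated unevenly: the synopsis and Section 7.1.1 include the test, while Section 4.2.2 and Table 4 do not. These passages must be reconciled.

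**3. Shift in the geometric mean.** The GMT is the exponentiated mean of the logs. If k of n participants have titers multiplied by F, the GMT is multiplied by F^(k/n). The GMFR shifts by the same factor, since the baseline value precedes infection. The documents do not give F, so a range is assumed.

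| F (assumed) | 1 of 12 | 2 of 12 | 5% of placebo arm, Month 7 |
|---|---|---|---|
| 10 | 1.21 | 1.47 | 1.12 |
| 50 | 1.39 | 1.92 | 1.22 |
| 100 | 1.47 | 2.15 | 1.26 |

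The 4-fold-rise percentage can move by 1/12 = 8.3 points or 2/12 = 16.7 points if those people would not otherwise have responded. In the Part 2 placebo arm it can move by up to 5 points. The Part 2 column treats 5% of placebo participants as infected by Month 7 with no waning of F.

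**4. Sampling error for scale.** At n = 12 the 95% half-width is 10^(0.635 × SD), where 0.635 = t/√12 on 11 df. For an assumed SD of 0.3 to 0.6 log10 this is 1.55- to 2.41-fold; for the ratio of two such groups it is 1.79- to 3.22-fold. One infection stays inside these limits across the assumed range. Two with a large rise can exceed one group's half-width: 1.92 against 1.55 at SD 0.3, and 2.15 against 2.08 at SD 0.5.

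**5. Chance of infection in a group of 12.** Reading 5% as a 26-week risk, the 8-week risk is 1 − 0.95^(8/26) = 1.6%. The chance of at least one infection is 1 − 0.95^(12 × 8/26) = 17%, and of two or more about 1.5%. If the 8-week risk were 5%, these become 46% and 12%; at 10%, 72% and 34%. Section 7.1.1 calls rates at the sites high but gives no figure.

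**6. Month 13, Part 2.** If a fraction q of the placebo arm is vaccinated before the Month 13 visit, the placebo GMT is multiplied by F^q, with F now the rise from that vaccine. The documents give no uptake, so this is not sized.

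**7. Does it reach dose selection?** Three statements disagree. Section 1.1 places the IDMC review after the active portion of Part 1, when Week 4 and Week 8 titers exist. Section 3.2.1 places it at completion of enrollment, when the last groups need not have reached those visits. Section 3.2.3 says Day 8 immunogenicity data will decide. Table 3 schedules no serum IgG/IgA or neutralizing titer at Day 8, only T cell responses and fixed whole blood.

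**The case against.** The strongest reply is that the plan is silent and has not decided to keep these samples. Section 8.3 leaves populations and the handling of spurious data to a SAP whose text is not in the documents, and important deviations could be defined to cover infection. That stands as a limit on the claim. It does not remove the gap: Section 8.2 already writes the sets out, and read as they stand they include these participants.

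Two stronger readings are tempting, and the documents do not support them.
- A reader might infer that infection-driven titers will decide the Part 2 dose. Only the Section 1.1 timing clearly allows it; under Section 3.2.3 no serum titer is available.
- A reader might infer that dose is confounded with epidemic wave, because low-dose groups 1a and 2a enroll before high-dose 1b and 2b. The gate is only Week 1 safety data, so 8-week active periods can overlap, and low-dose 1c and 2c open at the same gate as the high-dose groups, though in older adults. Differing infection pressure is possible, but no figure shows it.

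It is also fair to say that the IDMC already sees some COVID-19 events through safety data, and that Part 2 immunogenicity is descriptive by arm, with no vaccine-to-placebo GMT ratio or test planned. Both reduce the harm. Finally, dropping post-infection samples in Part 2 conditions on an event after randomization that the vaccine may influence. If vaccinated participants who become infected are the weaker responders, exclusion raises the vaccine GMT. That objection stands and shapes the fix.

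**Conclusion.** The gap is real in both Parts and worth closing before the analyses are run. Following Sections 8.2 and 8.3 as written pools responses to infection or another vaccine with the response to study vaccine.

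The size is modest for a single infection in a Part 1 group and material for two with a large rise. It rests on an assumed F of 10 to 100, applied alike to naive and previously vaccinated participants, an assumed SD of 0.3 to 0.6 log10, and the 5% attack rate read as a 6-month risk. That a single infection usually falls inside the confidence interval does not excuse it: the shift is upward, and the interval does not correct for it. In Part 2 the Month 7 effect on placebo is small, and the Month 13 effect depends on vaccine uptake.

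No effect on the choice of dose can be asserted until the three statements on its timing are reconciled.

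**What to change.** In Sections 8.2 and 8.3, for both Parts:
- Exclude from the main GMT/GMC, GMFR and 4-fold-rise summaries every sample collected after a confirmed SARS-CoV-2 infection (positive PCR or rapid molecular test), or after any COVID-19 vaccine other than the assigned study doses, which covers both options in Section 5.9.
- Keep the all-samples version as a supportive table and always report it alongside, since in Part 2 the exclusion conditions on a post-randomization event.
- Give the IDMC both versions for Part 1, with the number of infected participants per group.
- Define important deviations, and reconcile Sections 1.1, 3.2.1 and 3.2.3 on when, and on which data, the dose is selected.

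The cost is wording and one extra table set; no sample size changes. Precision falls a little: at an assumed SD of 0.5 log10 the 95% half-width goes from 2.08-fold at n = 12 to 2.17-fold at n = 11 or 2.28-fold at n = 10. The rule will miss undetected asymptomatic infections, because testing between dosing visits depends on reported symptoms or exposure, and the tables should say so.
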